Thus while BCL-2:venetoclax interactions may still be occurring in venetoclax-resistant AML cells, it appears other mechanisms are likely preventing these cells from undergoing apoptosis, for example, upregulation of MCL-1 or BCL-XL. One may (simplistically) model intrinsic apoptosis as being prevented by the summation of these 3 important proteins, MCL-1, BCL-XL and BCL-2, thus the binding of BCL-2 by venetoclax should still aid apoptotic stimuli in that it reduces the total amount of anti-apoptotic proteins in venetoclax-resistant cells. As an example of this the downregulation of MCL-1 by omacetaxine has been shown to overcome venetoclax resistance, resensitizing leukemia cells to *BCL-2 inhibition by venetoclax*. In addition, calicheamicin is a potent driver of apoptosis, in contrast to HMA, which, at the doses used in the venetoclax/HMA regimen, are not directly cytotoxic. Thus, by using Gemtuzamab to increase the apoptotic stimulus, requiring increased levels of anti-apoptotic proteins, previously venetoclax-resistant cells should be induced to undergo apoptosis.

In sum, we hypothesize that recruiting patients into BTCRC AML17-113 cohort 3 who are resistant to venetoclax is a therapeutically rational choice for the following reasons:

- (1) This cohort uses a dose of venetoclax, 600 mg, higher than the dose given with HMA (400 mg). Greater downregulation of BCL-2 should expose AML cells to greater apoptotic pressure.
- (2) GO should provide a greater stimulus to apoptosis, and the continued use of venetoclax means GO should provide this stimulus without being inhibited by BCL-2.
- (3) As TP53 mutations or deletions decrease the efficacy of GO, patients with AML who have been exposed to venetoclax AND who have developed TP53 mutations/deletion are likely not good candidates for this trial.

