# **3.2** Exclusion Criteria

Subjects meeting any of the criteria below may not participate in the study:

- Patients with history of prior use of GO or Venetoclax
   NOTE: Starting with dose cohort 3, prior therapy with venetoclax is allowed, provided patients
   do not have evidence of p53 deletion or mutations. If the dose cohort is de-escalated to dose
   cohort 2 due to toxicity in cohort 3, prior exposure to venetoclax will continue to be allowed,
   provided patients do not have evidence of p53 deletion/mutations.
- 2. History of myeloproliferative neoplasm [MPN] including myelofibrosis, essential thrombocythemia, polycythemia vera, CML with or without BCR-ABL1 translocation, and AML with BCR-ABL1 translocation.
- 3. More than three lines of prior therapy. A line of therapy consists of ≥1 complete cycle of a single agent, a regimen consisting of a combination of several drugs, or a planned sequential therapy of various regimens (e.g., 3-6 cycles of initial therapy with bortezomib-dexamethasone [VD] followed by stem cell transplantation [SCT], consolidation, and lenalidomide maintenance is considered 1 line).
- 4. WBC >25  $\times$  10^9/L. Cytoreduction is required (hydroxyurea as per local standard of care).
- 5. Acute promyelocytic leukemia.
- 6. Unresolved  $\geq$  grade 2 clinically significant nonhematologic toxicities from prior anticancer therapy or *unresolved* disseminated intravascular coagulation  $\geq$  grade 2 per CTCAE v5 criteria.
- 7. History of other malignancies within 1 year prior to study entry, with the exception of: adequately treated *in situ* carcinoma of the cervix uteri or carcinoma *in situ* of breast; basal cell carcinoma of the skin or localized squamous cell carcinoma of the skin; previous malignancy confined and surgically resected (or treated with other modalities), with curative intent.
- 8. Investigational drug within 4 weeks of study entry.
- 9. History of CHF requiring treatment, left ventricular ejection fraction ≤ 50%, cardiac insufficiency grade III or IV per New York Heart Association classification (NYHA; see Appendix II), or chronic stable angina
- 10. Patients who are HIV positive.
- 11. Known CNS involvement with AML.
- 12. Previous hematopoietic stem cell transplant within 2 months.

- 13. Previous history of veno-occlusive disease/sinusoidal obstruction syndrome.

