# 5.3 Dose Cohorts

# 5.4 Induction (Cycle 1) and Consolidation (Cycle 2):

Cycle 1: Gemtuzumab Ozogamicin (GO) 3 mg/m^2 IV infusion (up to one 4.5 mg vial) will be given on days +1, +4, and +7 in combination with daily oral administration of Venetoclax during Induction. Based on previous studies, Venetoclax dose will start at 200 mg daily with dose escalation planned over 3 cohorts to identify the recommended phase 2 dose (RP2D). Dose cohort 3 will use the maximum dose of Venetoclax of 600 mg orally daily. Because of evidence of tumor lysis syndrome (TLS) with Venetoclax use in previous CLL studies, we will use a 3-day stepwise ramp up in cycle 1 to the target dose for all cohorts (see Table 1). Patients should expect to be hospitalized throughout Induction/Cycle 1, although medically stable patients may be discharged from the hospital under close supervision at the discretion of the treating physician. Patients do not have to be hospitalized during the first week of consolidation if the treating physician wishes to administer Gemtuzumab (C2D1 and D4) in the outpatient clinic.

Day	Cohort 1 (mg)	Cohort 2 (mg)	Cohort 3 (mg)
-2	50	50	100
-1	100	100	200
0	100	200	400
1–28	200	400	600

Table 1. Venetoclax Ramp-up schedule

Clinical and hematological responses will be assessed after the end of both the induction and consolidation cycles. Bone marrow assessment will occur on day 28 regardless of absolute neutrophil count (ANC) or platelet recovery.

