# 12.6.2 Analysis Plans for Secondary Objectives

Descriptive characteristics of all adverse effects of GO in combination with Venetoclax (using CTCAE v5 criteria) will be reported; and the efficacy of the combination in achieving ORR (includes CR/CRi) and anti-leukemic activity (includes CR/CRi/PR), as defined by the revised IWG criteria), RFS, EFS, and OS in subjects. The effects of therapy on quality of life, fatigue, and physical function at D0 (trial entry) and the end of every other month for 1 year (see section 8.1) will be reported and analyzed using generalized linear modeling.

All time-to-event outcomes (e.g. survival) will be calculated using Kaplan Meier methods and exploratory log-rank tests will be used to compare treatment effect between groups based on genomic MRD, CD33 DNA polymorphisms, BH3 profiling and anti-apoptosis protein levels in PB MBCs at presentation and after 1 week of Venetoclax.

*Sample size permitting:* Hazard ratios (HR) and 95% CIs will be produced. Time-to-event outcomes with a competing or semi-competing risk (e.g. CIR) will be analyzed using cumulative incidence curves and exploratory comparisons between arms will be made using Grey's test. Rate ratios and 95% CIs will be presented. Chi squared tests will be used to assess the treatment effect between cohorts for all categorical variables and t-tests or Mann Whitney tests will be applied for continuous measures as appropriate.

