# **12.6.3 Other Planned Analyses**

Descriptive characteristics of patients will be reported in tabular form along with the dates of trial opening and closing, indicating the total number of patients enrolled and accounting for all patients considered for entry (flow diagram). Patients found to be ineligible will be indicated along with their reasons for ineligibility and whether they received any study therapy. Of the included subjects, the number of patients who were evaluable for toxicity and response (secondary objectives, see section **12.2.2**) will be reported.

Drug administration by dose level will be reported in tables detailing the total number of patients treated, number of doses or cycles received at dose level, and the number of incomplete cycles, including brief descriptions of what happened in dose escalation if intermediate dose levels or deviations from study protocol resulted. Any dose holds, reductions, and delays, and permanent discontinuation of study treatments will be summarized with reasons for each. Finally, summaries of dose intensity will be estimated, including how many patients were able to receive each planned dose intensity of Venetoclax administered with Gemtuzumab Ozogamicin.

Tables of adverse effects displaying the worst grade by dose level will be reported, including columns or each grade and "any grade" adverse effects. Separate tables report hematological and non-hematological effects will be reported according to dose escalation.

Descriptive tables reporting frequencies and means or medians of scores of the EORTC QLQ-C30 and FACT-Fatigue questionnaire, two-minute walk test, and timed chair stand will be created for D0 (trial entry) and subsequent months of follow up. Generalized linear modeling of continuous scores or ordinal values accounting for correlation and repeated will be performed to determine differences between groups

and characteristics considered to be potential confounding factors. Given a threshold value indicating a substantial degree of the outcome (i.e., quality of life, fatigue and physical function), generalized estimating equation models with a binomial distribution and unstructured correlation covariance will be used to produce odds ratios (OR) and robust 95% CI for the relation of dose and clinical characteristics to each outcome.

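### If cohort 3 opens, prior venetoclax becomes admissible at the same step as the top dose, so between-cohort comparisons and the pooled RP2D response rate mix dose with prior exposure

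*Combined protocol and SAP*

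**What the plan says.** **Eligibility.** Section 3.2 excludes prior use of GO or venetoclax, with one exception: "Starting with dose cohort 3, prior therapy with venetoclax is allowed", provided there is no p53 deletion or mutation. If toxicity in cohort 3 sends the study back to cohort 2, "prior exposure to venetoclax will continue to be allowed" on the same p53 condition. No such condition applies to venetoclax-naive patients.

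**Dose.** The exception begins at the highest level: "Dose cohort 3 will use the maximum dose of Venetoclax of 600 mg orally daily" (Section 5.4). Section 1.3.1 shows that the change is deliberate, since it argues for "recruiting patients into BTCRC AML17-113 cohort 3 who are resistant to venetoclax".

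**Analysis.** Section 12.6.2 states that "Chi squared tests will be used to assess the treatment effect between cohorts for all categorical variables", with t or Mann-Whitney tests for continuous measures. That paragraph is conditional on sample size. Sections 12.5 and 12.6.2 report response (CR/CRi), anti-leukemic activity (CR/CRi/PR) and survival without a split by prior venetoclax. Section 12.6.1 presents DLTs by dose. Section 12.6.3 plans odds ratios with "robust 95% CI for the relation of dose and clinical characteristics to each outcome", where the outcomes are quality of life, fatigue and physical function. It refers in general terms to "characteristics considered to be potential confounding factors". Section 12 nowhere names prior venetoclax as a stratum, subgroup or covariate.

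**The concern.** A comparison of 600 mg with the lower doses is informative about dose only if the patients are otherwise alike. Here the admissible population changes at exactly the step where the dose changes. A difference in response between cohort 3 and cohorts 1–2 could come from the dose, from prior exposure, or from both, and the planned tests cannot tell which. A real dose effect could be hidden, or an apparent one created.

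The second consequence concerns the expansion. Section 5.1 adds six patients at the RP2D to learn more about efficacy and safety. If the RP2D is 600 mg, or 400 mg after de-escalation from cohort 3, its single response rate averages over an uncontrolled mix of naive and pretreated patients. After de-escalation, cohort 2 could itself pool naive patients from escalation with pretreated patients enrolled later. A later study planned from that rate would not know which population it describes.

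**Working it through.** The documents give no figure for this effect, so there is none to reproduce. The target quantiles in Section 12.3 concern DLT rates and do not bear on it.

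**Inputs**
- *f*, the pretreated share of cohort 3: not in the documents, varied from 0 to 1.
- *p_n*, response in naive patients: assumed 0.33 to 0.70. The ends are borrowed from Section 1.2: 33% for fractionated GO alone in relapsed AML, and over 70% for venetoclax with a hypomethylating agent in de novo AML. The upper end is generous for this population.
- *p_p*, response in pretreated patients: assumed 0.10 to 0.20, with no source in the documents.
- Sizes: 6 patients in cohorts 1–2 (3 + 3, no DLTs) against 12 at 600 mg (6 in escalation + 6 in expansion).
- Test: uncorrected chi-squared at two-sided 0.05. The plan states no level, so this is also an assumption.

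**Step 1. Spurious difference with no dose effect.** Expected response in cohort 3 is (1 − f)·p_n + f·p_p. Cohorts 1–2 have p_n. The difference is −f·(p_n − p_p).

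| p_n | p_p | f | Cohort 3 response | Difference | Odds ratio | Test rejects (6 vs 12) |
|---|---|---|---|---|---|---|
| 0.33 | 0.20 | 0.5 | 0.265 | −0.065 | 0.73 | 0.086 |
| 0.33 | 0.10 | 0.5 | 0.215 | −0.115 | 0.56 | 0.127 |
| 0.70 | 0.20 | 0.5 | 0.450 | −0.250 | 0.35 | 0.196 |
| 0.70 | 0.10 | 0.5 | 0.400 | −0.300 | 0.29 | 0.263 |
| 0.33 | 0.20 | 1 | 0.200 | −0.130 | 0.51 | 0.144 |
| 0.70 | 0.10 | 1 | 0.100 | −0.600 | 0.05 | 0.846 |

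Rejection rates are exact enumerations. With f = 0 the same test rejects in 0.060 to 0.067 of trials, which is its small-sample level. At half pretreated, the spurious drop among 12 patients is 0.065 × 12 = 0.8 to 0.30 × 12 = 3.6 responders.

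**Step 2. Sign.** The difference is negative only because p_p is assumed to be below p_n. If p_p were above p_n, the same formula would give a spurious gain.

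**Step 3. Masking.** Suppose 600 mg truly adds 0.20 in both groups (naive 0.33 to 0.53, pretreated 0.13 to 0.33). At f = 0.5, cohort 3 shows 0.5 × 0.53 + 0.5 × 0.33 = 0.43, an apparent gain of 0.43 − 0.33 = 0.10. At f = 1 it shows 0.33, an apparent gain of 0.

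**Step 4. Can the two be separated?** Comparing naive patients only removes the expected spurious difference, provided some naive patients are treated at 600 mg. If f = 0.75, the chance that none are is 0.75^6 = 0.18 for six patients and 0.75^12 = 0.03 for twelve. At f = 1, dose and prior exposure cannot be separated by any analysis.

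**The case against.** Much of the case on the other side stands.

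- **Decisions.** A reader might infer that dose selection is compromised. It is not affected by the efficacy comparisons: Sections 5.1 and 12.3 set the MTD and RP2D from DLT counts. The documents also give no reason to expect a different DLT risk in pretreated patients, so a DLT split is only descriptive.
- **Direction.** A reader might infer that the protocol expects pretreated patients to respond worse, so that 600 mg will look too poor. Section 1.3.1 does not say so; it argues that GO should drive resistant cells into apoptosis. The p53 condition applies only to pretreated patients, and the same section says that GO is less active with TP53 mutations. That difference in case mix could favour the pretreated group.
- **Dose models.** A reader might take the dose models in Section 12.6.3 to be unadjusted models of response. They cover quality of life, fatigue and physical function only, and they provide for confounders and clinical characteristics. What is missing there is the name of the variable.
- **Status and reach.** The between-cohort tests are secondary and depend on sample size, with 3 to 6 patients per escalation cohort. If cohort 3 never opens, the problem does not arise. Naive patients may still enter cohort 3, so the confounding need not be complete.
- **Size.** The rates are assumptions. With 40% naive and 15% pretreated, response at 600 mg would be 27.5% with half pretreated and 21.25% with three quarters. The 6 versus 12 test would reject in 12% and 19% of trials, against 6.5% with no difference. A falsely significant result is therefore not the likely outcome in that scenario.

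These points limit the concern but do not remove it. Small samples do not cure bias, and the Section 12.6.2 tests and the RP2D response rate have no stated route for adjustment.

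**Conclusion.** The point holds, conditional on cohort 3 opening. Eligibility and top dose change together, and the planned between-cohort tests and pooled RP2D response rate do not distinguish them. This follows from Sections 3.2, 5.4 and 12.6.2 and does not depend on any assumed rate.

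The size and sign of the bias do depend on assumptions and are unknown. The 6.5 to 30 point drop illustrates one direction, with half of cohort 3 pretreated. The harm is to the interpretation of secondary efficacy results and to what the expansion can tell a later study. It does not reach the rule that selects the dose.

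**What to change.** - **Section 12.6.2:** report response, anti-leukemic activity and survival by prior venetoclax (yes/no) within each dose level. Show the RP2D response rate split as well as pooled. Make any between-cohort comparison in venetoclax-naive patients only, or report it descriptively, without a test, if too few naive patients are treated at 600 mg.
- **Section 12.6.1:** show the DLT table with the same split, for description only.
- **Section 12.6.3:** name prior venetoclax as a covariate in the dose models for quality of life, fatigue and physical function.

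The study calendar already records prior therapy at screening, so this costs wording and table layout, with no new data, patients or visits. The price is small strata and wide intervals. If nearly all patients at 600 mg turn out to be pretreated, the split tables will show that dose and prior exposure cannot be separated, and the report should say so.

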#### 4. SUBJECT REGISTRATION

All subjects must be registered through Big Ten Cancer Research Consortium (Big Ten CRC) Administrative Headquarters'(AHQ) electronic data capture (EDC) system. A subject is considered registered when an 'On Study' date is entered into the EDC system.

Registration will occur after the patient has signed the patient consent and eligibility is confirmed, but before any treatment has been administered. To be eligible for registration to this study, the patient must meet each of the criteria listed on the eligibility checklist. A copy of the eligibility checklist will be retained at the participating center. Subjects must begin therapy within **5 business days** of registration.

Venetoclax dose levels will be assigned at registration.

If a patient signs consent and is registered to the study and is later found to be unable to begin the planned study treatment, for whatever reason, the patient will be removed from study and treated at the physician's discretion. The patient will be considered a screen/baseline failure and be replaced. Further data will not be collected if the patient has not begun study treatment at the time of removal from trial. The reason for removal from study will be clearly indicated in EDC.

If a patient begins treatment, and then treatment is discontinued for whatever reason, the patient must be followed per section 7.2.

# 5. TREATMENT PLAN

This will be a single arm, open-label multicenter study of the combination of Venetoclax and GO in patients with AML. It will be an initial dose-escalation phase Ib study (Cohorts 1-3); using a standard 3+3 design to determine the maximum tolerated dose. There will be an induction and a consolidation cycle followed by a maintenance phase.

# 5.1 Dose Escalation Rules

- Three to six subjects will initially be enrolled at dose level 1. If none of the 3 subjects experience a dose limiting toxicity (DLT) during the first cycle of therapy, an additional three subjects will be enrolled at dose level 2. If none of the 3 subjects at dose level 2 experience a dose limiting toxicity (DLT), an additional three subjects will be enrolled at dose level 3. If all subjects in dose level 3 complete the first cycle of therapy without DLT, 3 more subjects will be enrolled into dose level 3 to ensure only 0-1 of 6 subjects have a DLT. There will be no further escalation beyond dose level 3.
- Alternatively, if 1 of the first 3 subjects within any given dose cohort experiences a DLT, an additional 3 subjects will be enrolled at that dose level. If only 1 of the total 6 subjects in a dose level experience a DLT, the study will proceed to the next dose level as planned. If 2 of the total 6 subjects in any given dose cohort experience a DLT, the next lower dose level will be explored and considered the maximum tolerated dose (MTD) if no more than 1 of 6 subjects experience a DLT. If this occurs in cohort 1, the dose will be decreased to cohort -1 and if 2 or more DLTs are reached in dose level -1, the study will be put on hold and a protocol amendment will be considered. [see Section 6.4 for "Stopping Rules"]
- The MTD for Venetoclax in combination with Gemtuzumab Ozogamicin is defined as the dose level at which fewer than 33% of subjects experience a dose limiting toxicity (DLT), and specifically is the dose level at which less than 2 out of 6 subjects experience DLT. That dose will be the recommended Phase II dose (RP2D).
- Once the RP2D has been identified, we will expand this cohort to include an additional six patients to further evaluate the efficacy and safety profile of the RP2D.

# 5.2 Definition of Dose-limiting Toxicities

Dose-limiting toxicities (DLTs) are defined as an adverse event related (possible, probable or definite) to Venetoclax and/or Gemtuzumab Ozogamicin fulfilling one of the following criteria:

 Hematologic toxicity: treatment-related grade 3 or worse neutropenia and/or thrombocytopenia due to bone marrow hypocellularity present at the end of cycle one (day 28) with an additional 28 days allowed for count recovery (i.e. present at day 56); specifically grade 3 or worse neutropenia or thrombocytopenia with the bone marrow documented to be free of leukemic infiltration. Note: patients who enter the study with grade 3 or worse cytopenias will not be evaluable for hematologic dose-limiting toxicities.

• Non-hematologic toxicity: any grade 3 or worse treatment-related toxicity occurring within the first cycle (excluding grade 3-4 infections during cycle one).

# NOTE: Events that can be clearly attributed to disease progression, concurrent illness or the effects of other medications will not be classified as DLTs.

DLTs will be counted based on the number of patients with a DLT at a given dose level, not the absolute number of DLTs. No single patient can trigger more than one DLT. Intra-patient dose escalation is not permitted.

Cohort	Number of Subjects	Venetoclax Daily Dose (mg)	Gemtuzumab Ozogamicin IV on Days +1, +4, +7
-1	3-6	100	
1 (start)	3-6	200	$3 \text{ mg/m}^2$
2	3-6	400	(up to one 4.5 mg vial)
3	3-6	600	

# 5.3 Dose Cohorts

# 5.4 Induction (Cycle 1) and Consolidation (Cycle 2):

Cycle 1: Gemtuzumab Ozogamicin (GO) 3 mg/m^2 IV infusion (up to one 4.5 mg vial) will be given on days +1, +4, and +7 in combination with daily oral administration of Venetoclax during Induction. Based on previous studies, Venetoclax dose will start at 200 mg daily with dose escalation planned over 3 cohorts to identify the recommended phase 2 dose (RP2D). Dose cohort 3 will use the maximum dose of Venetoclax of 600 mg orally daily. Because of evidence of tumor lysis syndrome (TLS) with Venetoclax use in previous CLL studies, we will use a 3-day stepwise ramp up in cycle 1 to the target dose for all cohorts (see Table 1). Patients should expect to be hospitalized throughout Induction/Cycle 1, although medically stable patients may be discharged from the hospital under close supervision at the discretion of the treating physician. Patients do not have to be hospitalized during the first week of consolidation if the treating physician wishes to administer Gemtuzumab (C2D1 and D4) in the outpatient clinic.

Day	Cohort 1 (mg)	Cohort 2 (mg)	Cohort 3 (mg)
-2	50	50	100
-1	100	100	200
0	100	200	400
1–28	200	400	600

Table 1. Venetoclax Ramp-up schedule

Clinical and hematological responses will be assessed after the end of both the induction and consolidation cycles. Bone marrow assessment will occur on day 28 regardless of absolute neutrophil count (ANC) or platelet recovery.

After induction, patients demonstrating complete remission or partial remission will continue to consolidation. Patients in CRi (ANC <  $1.0 \times 10^9$ /L or platelets <  $100 \times 10^9$ /L) will stop Venetoclax for up to four weeks to allow for cytopenia recovery. If the ANC recovers to  $\ge 1.0 \times 10^9$ /L and the platelets recover to  $\ge 100 \times 10^9$ /L, consolidation will ensue. If there is not full ANC AND platelet recovery to the aforementioned levels, consolidation will be omitted, and patients will enter the maintenance phase with Venetoclax alone provided they do not have any grade 3-4 cytopenias. The previously assigned Venetoclax dose will be resumed and the maintenance rules for Venetoclax dose adjustments or discontinuation will apply (see section 6.2.2). If however patients have a grade 3-4 cytopenia despite holding Venetoclax for four weeks, they will be *removed from study* [NOTE: this applies to both induction and consolidation.]

Cycle 2: The second cycle (consolidation) will consist of GO 3 mg/m^2 IV infusion (up to one 4.5 mg vial) on days +1, and +4, in addition to daily oral administration of Venetoclax at the assigned dose. A bone marrow assessment will occur on day 28 regardless of cytopenias and those with CR, CRi, or at least a partial remission will continue onto maintenance therapy with Venetoclax alone. The previously assigned Venetoclax dose will be resumed and the maintenance rules for Venetoclax dose adjustments or discontinuation will apply (see section **6.2.2**).

After day 28, in the absence of leukemia in the BM, where there is a grade 3-4 cytopenia (thrombocytopenia or neutropenia), Venetoclax should be held for up to four weeks to allow recovery of counts to platelets  $\geq 50 \times 10^9$ /L and ANC  $\geq 1.0 \times 10^9$ /L (to allow entry into Maintenance Phase). Those who continue to have a grade 3-4 cytopenia will be taken off study.

Patients with treatment failure (see Section 9.1) will be taken off study. Please note that any patient with residual disease (with at least PR) may move onto consolidation regardless of blood counts.

